1. To compare the recovery to a 50 units/kg ($\pm 20\%$) dose of factor VIII (FVIII) concentrate in participants age 12 and above with hemophilia A when calculated on *actual body weight (ABW)* versus *ideal body weight (IBW)*.
2. To determine the likelihood of under dosing when using IBW or over-dosing with ABW

Secondary outcomes:

[figure not shown]
- To determine the effect on half-life of these dosing strategies
- To determine the effect on PK differences of hemophilia severity
- To determine differences in participants receiving half-life (HL) vs. extended half-life (EHL) products
- To determine the differences, if any, between overweight and obese participants

Inclusion Criteria

- At least 12 years of age
- Hemophilia A
- Male gender
- Able and willing to comply with PK testing schedule
- Either overweight or obese BMI (using CDC definitions by age)

Table 1: The standard weight status categories associated with BMI ranges for adults (≥ 20 year old)

BMI	Weight Status
Below 18.5	Underweight
18.5 – 24.9	Normal or Healthy Weight
25.0 – 29.9	Overweight
30.0 and Above	Obese

Figure 1: The standard weight status categories associated with BMI ranges for boys (2 to 19 years)

Exclusion Criteria

- Inhibitor of > 0.6 BU twice in the past, or documented abnormal recovery of less than 66% (of expected) in the past.
- Known other bleeding disorder
- Known other prolongation in aPTT (lupus anticoagulant, FXII deficiency)
- Female gender

Recruitment

Participants will be recruited through the participating centers. Washington Center for Bleeding Disorders (WCBD), Oregon Health & Science University (OHSU), Seattle Children's Hospital (SCH) and Providence Sacred Heart Children's Hospital (SH). Cumulatively, up to 20 patients will be enrolled at all 4 sites.

Randomization

Randomization will be performed centrally at the Washington Center for Bleeding Disorders. When a participant has completed the consent and eligibility forms and is able to be enrolled, the participating center will contact WCBD to receive the subject ID and treatment arm assignment. Randomization will be determined by

blocked randomization. Subjects will be randomized to either undergo PK measurements based on actual body weight followed by ideal body weight OR PK measurements based on ideal body weight followed by actual body weight.

Study design - Primary outcome:

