Participants age 12 and up and considered to be overweight or obese by either calculated BMI (ages 20 and over) or the McLaren method (ages 12 to 19) and diagnosed with hemophilia A of any severity will be enrolled.

There must be a period of at least 48 hours for standard half-life products or at least 72 hours for extended half-life products since the last dose of factor. Participants will be randomized to receive 50 U/kg ($\pm 20\%$) of the factor product they routinely use either based on IBW or ABW and will have pharmacokinetic (PK) labs drawn as described in the PK protocol section. After a period of at least 48 hours for standard half-life products or at least 72 hours for extended half-life products but no more than 60 days, participant will receive a second dose of factor at 50 U/kg ($\pm 20\%$) based on the alternate dosing strategy and will have a second set of PK labs drawn.

Patients may bring and infuse their own factor, have it infused by their parents or by the clinic staff. Should there be bleeding during the study, the bleed should be treated as per the patient's usual protocol.

PK studies will be delayed until the resolution of any acute bleeding episodes [after a period of at least 48 hours for standard half-life products or at least 72 hours for extended half-life products]. If the participant has an acute bleed after the recovery draw, then that episode will not be used in the analysis. The episode will be attempted again at a later date within the 2-month window.

Intention to treat:

If a participant experiences a 10% or greater change in BMI between the first and second dose, the participant will be included in the analysis.

Minimum of 8 participants ages 12 and over

Ideal body weight and BMI calculations:

BMI Calculations:

Sites shall use CDC website to calculate BMI for all participants and to determine if participants are overweight or obese.

Ages 12 to <20: <https://nccd.cdc.gov/dnpabmi/Calculator.aspx>

[figure not shown]
Ages 20 and older:

http://www.cdc.gov/healthyweight/assessing/bmi/adult_bmi/metric_bmi_calculator/bmi_calculator.html

IBW Calculations:

Ages 12 to <20: Sites shall use the McLaren method to calculate ideal body weight in participants under 20 years old. [Phillips et al 2007]

<http://www.cdc.gov/growthcharts/data/set1clinical/cj41c021.pdf>

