Ages 20 and older: Sites shall use the following equation to calculate IBW in participants 20 years and older: $IBW = 50 \text{ kg} + (2.3 \text{ kg} * \text{every inch over 5 feet})$

PK Protocol:

PK studies will be measured in response to one 50 U/kg ($\pm 20\%$) dose of the participant's current product. Every effort shall be made to ensure the same size

vials and same lot numbers are used with the second dose to ensure the second dose is as similar to the first dose as possible. All participants will undergo PK testing twice: One test will be with 50 U/kg ($\pm 20\%$) for hemophilia A based on ideal body weight and the other test will be with 50 U/kg ($\pm 20\%$) for hemophilia A based on actual body weight.

Post dose blood draws cannot be pulled from the port/IV that was used to administer factor. Sites may infuse factor through a peripheral line and obtain post blood draws through a port.

Blood Draw Policy and Schedules: The baseline and the recovery draws for the first and second doses must be completed by the same laboratory (baseline laboratory). Baseline and peak (recovery) levels will be drawn in duplicate. The Duplicate draw will be spun and frozen for batch shipping/testing at the designated “reference” lab. Duplicate samples from OHSU and Seattle Children’s will be tested at WCBD, Duplicate samples from WCBD and Scared Heart will be tested at OHSU.

Blood draws to measure half-life are encouraged to be drawn in the baseline laboratory, but may be drawn in other local laboratories and shipped to the baseline laboratory for analysis. If the 30-minute recovery draw is missed participant can still be included with another attempt of the dose/PK draw if the second dose/draw falls within the 2 month window.

Hemophilia A – regular half-life product

Baseline – 30 \pm 10 minutes – 5 to 7 hours – 20 to 26 hours – 44 to 50 hours

Hemophilia A – extended half-life factor

Baseline – 30 \pm 10 minutes – 5 to 7 hours – 20 to 26 hours – 44 to 50 hours – 69 to 75 hours – 93 to 99 hours

Statistics:

The first primary endpoint will be assessed by evaluation of the mean paired difference in recovery between the two methods (IBW vs. ABW dosing) by paired t-test or by Wilcoxon signed-rank test if recoveries are skewed.

The second primary endpoint will be evaluated by extension of estimated recovery distribution to estimate the likelihood of failure (under-dosing or over-dosing) of each dosing strategy.

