For the first of the above evaluation measures, assuming approximate normality of recoveries, we estimate having 80% power to detect a mean reduction of 1 standard deviation in a study of 16 subjects assuming an intra-class correlation of at least 0.2. Greater (lesser) intra-class correlation would increase (decrease) statistical power for this evaluation.

In the event that the study is underpowered (due to a lower than anticipated intra-class correlation), distributional summaries for each approach and for paired differences (including histograms) as well as for the intra-class correlation would be useful for design of future studies if the ideal weight base factor dosing is not deemed unacceptable

Collecting and Reporting Adverse Events:

Serious adverse events are defined as when the patient outcome is either death, life-threatening, hospitalization (initial or prolonged), disability or permanent damage, congenital anomaly/birth defect, required intervention to prevent permanent impairment or damage, or other serious, important medical events. Serious adverse events should be tracked per patient and reported centrally to the [Washington Center for Bleeding Disorders](#). Adverse events that do not meet the criteria for serious adverse events but qualify as Grade 3 or 4 adverse events will be recorded and reported.

Information to collect and report on adverse events includes patient details, suspected medicinal product, other treatments, details of suspected adverse reactions, details on the reporter of the event.

Funding: This research is funded by the Healthcare Authorities of Washington

References

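### Does the unexplained minimum of 8 participants undercut the 80% power that the protocol states for 16?

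*Protocol*

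**What the plan says.** Three participant numbers appear in three places in the protocol.

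- **Floor.** Within Study design - Primary outcome, at the end of the Intention to treat text, stands "Minimum of 8 participants ages 12 and over". It does not say whether the 8 are enrolled participants, completed pairs, participants per sequence or the whole study.
- **Planning number.** The Statistics section claims "80% power to detect a mean reduction of 1 standard deviation in a study of 16 subjects", "assuming an intra-class correlation of at least 0.2", and adds that "Greater (lesser) intra-class correlation would increase (decrease) statistical power for this evaluation".
- **Cap.** Recruitment states: "Cumulatively, up to 20 patients will be enrolled at all 4 sites".

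Two other statements bear on the reading. Inclusion Criteria requires "At least 12 years of age", so the age wording in the floor describes everyone eligible and picks out no subgroup. PK Protocol states "All participants will undergo PK testing twice", so each participant supplies one paired difference. The Statistics section also says what will be reported if power proves too low, naming one cause: "In the event that the study is underpowered (due to a lower than anticipated intra-class correlation".

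**The concern.** A printed minimum is easily read as the number at which the trial has done what it set out to do. Here it is half the number behind the power statement, and nothing explains the gap. On a whole-study reading, the trial could stop at 8, satisfy its protocol and have roughly even odds of detecting the reduction it was sized for. The question is whether low recovery under ideal-weight dosing would be noticed, so a non-significant result from 8 pairs could be mistaken for reassurance. The power text does not guard against this, because the only cause of low power it mentions is a low intra-class correlation (ICC), not a small number of participants.

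**Working it through.** **Inputs from the protocol.** Effect: 1 SD of recovery. ICC: at least 0.2. Sizes: 16 (planning), 8 (minimum), 20 (cap). Test: paired t-test, or Wilcoxon signed-rank if recoveries are skewed.

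**Assumptions.** Alpha and sidedness are not stated, so two-sided 5% is used, with one-sided 5% as the range. ICC 0.5 is illustrative. The sizes 8 and 16 are taken as evaluable pairs.

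**Formulas.** In units of the SD of recovery:

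- SD of the paired difference = √(2(1 − ICC)). This is √1.6 = 1.265 at ICC 0.2 and 1.00 at ICC 0.5.
- Noncentrality = √n / SD of the difference, with n − 1 degrees of freedom. Power comes from the noncentral t distribution.

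**Step 1: the protocol's own figure.** With n = 16 and ICC 0.2, the noncentrality is 4/1.265 = 3.16. Power is 84.0% by paired t-test and about 81% by Wilcoxon (simulated, normal data). The smallest n that reaches 80% by paired t-test is 15 (81.2%; 14 gives 78.1%). The stated 80% at 16 is sound.

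**Step 2: possible readings of the 8.**

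- Per site: 4 × 8 = 32, which exceeds the cap of 20, so this is ruled out.
- Per sequence: 2 × 8 = 16, which equals the planning number, so there is no shortfall.
- Whole study: 8 ≤ 16 ≤ 20. The numbers are compatible, but power at the floor is lower.

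**Step 3: power at n = 8 on the whole-study reading.** At ICC 0.2 the noncentrality is 2.828/1.265 = 2.24; at ICC 0.5 it is 2.83.

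| n = 8 | Paired t, two-sided | Paired t, one-sided | Wilcoxon, two-sided | Wilcoxon, one-sided |
|---|---|---|---|---|
| ICC 0.2 | 49% | 64% | 42% | 58% |
| ICC 0.5 | 68% | 82% | 61% | 76% |

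By paired t-test, 8 pairs reach 80% once ICC is about 0.63 (two-sided) or 0.48 (one-sided). At ICC 0.7 the two-sided power is 88%.

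**Step 4: precision.** The half-width of the two-sided 95% interval for the mean difference is the t quantile × SD of the difference / √n. At ICC 0.2 this is 1.06 SD for 8 pairs and 0.67 SD for 16. For 8 pairs it falls to 1 SD at an ICC of about 0.285 and to 0.84 SD at ICC 0.5. An observed difference of zero would therefore fail to exclude a 1 SD reduction only for ICC between 0.2 and about 0.285.

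**The case for a change.** The best argument for acting is that this is not a detail left to an analysis plan: the protocol itself prints the number and leaves it ambiguous beside another printed number. The literal reading is the whole study, since the line mentions no sequence or arm. On that reading, at the protocol's own ICC of 0.2, 8 pairs miss 80% whether the test is one- or two-sided. The loss also exceeds that from the one risk the protocol names: 16 subjects at an ICC of zero would still give 75% (paired t-test, two-sided), against 49% for 8 subjects at ICC 0.2.

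The arithmetic stands, and so does the ambiguity. What does not follow is that something in the plan must change. The protocol nowhere says that 8 is enough for the paired comparison, and it attaches no analysis, endpoint or stopping decision to that number. The summaries planned for an underpowered study (distributions, paired differences, the ICC) would serve equally well if the cause were few participants.

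The possible remedies gain little. Explaining the 8, or adding a second cause of low power, writes down a detail without altering any analysis. Making 16 the floor could mean up to 8 more participants and 2 × 8 = 16 more PK sessions, though no stated figure is missed. Describing anything below 16 as underpowered would be inexact, since 15 pairs still give 81.2% by paired t-test at ICC 0.2.

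**Conclusion.** No change follows. The minimum of 8 is unexplained, but it contradicts neither the 80% stated for 16 subjects, which reproduces, nor the cap of 20. On the per-sequence reading the shortfall is nil. On the whole-study reading, power at the floor for a 1 SD reduction is 49% two-sided or 64% one-sided at ICC 0.2, and 68% or 82% at ICC 0.5 (paired t-test, 5% alpha assumed). The protocol gives a lower bound for the ICC and no estimate of it, so the actual size of any shortfall is unknown.

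This is a small wording gap that a sensible analyst fills by reporting the number of pairs obtained and applying the 80% statement only to 16. If the protocol is revised for other reasons, a clause saying what the 8 counts would be a courtesy to the reader.

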Comparison of Ideal vs. Actual Weight Base Factor Dosing

Version 2.0

October 12, 2016

Comparison of Ideal vs. Actual Weight Base Factor Dosing

Background

Hemophilia is an x-linked (mainly affecting males) genetic disorder characterized by a mutation in the clotting factor VIII gene (hemophilia A) or the clotting factor IX gene (hemophilia B) resulting in spontaneous and trauma-induced bleeding. This bleeding can be treated and prevented with clotting factor concentrate which has been available since the 1960s. A randomized clinical trial published in 2007 [Manco-Johnson, NJEM 2007] established that prophylactic treatment with factor several times a week prevents bleeding and adverse clinical outcomes due to bleeding such as joint arthropathy. Thus, prophylactic treatment with clotting factor became standard of care.

Clotting factor replacement is given intravenously and is based on a patient's weight. The clotting factor circulates in the plasma with a half-life of hours to days (depending on the product). It does not get distributed in the adipose (fat) tissue. Although total plasma volume might increase with body mass index, it does not increase proportionally. The current standard of calculating a patient's dose on actual body weight may overestimate the appropriate dose, and calculations based on ideal body weight may be more accurate. Inappropriate dosing may not only be harmful for the patient but also leads to unnecessary health care cost.

Hypothesis: Factor dosing based on ideal body weight will result in hemostatic factor levels (recovery of at least 66% of predicted).

Null Hypothesis: Factor dosing based on ideal body weight will not result in hemostatic factor levels (recovery of at least 66% of predicted).

Trial Design

This is a randomized, prospective, multicenter, open-label, cross-over study comparing the pharmacokinetics (PK) of ideal vs. actual body weight dosing of factor concentrate in overweight and obese participants with hemophilia A.

The study will be conducted at the Washington Center for Bleeding Disorders (WCBD), Oregon Health & Science University (OHSU), Seattle Children's Hospital (SCH) and Providence Sacred Heart Children's Hospital (SH). Ethics approval will be obtained at each individual location before trial enrollment begins for that location.

Primary outcomes:

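### The primary paired test leaves out the period and sequence by which the trial randomises; if a period effect exists, the IBW–ABW interval is too wide, and unequal sequences bias the estimate

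*Protocol*

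**What the plan says.** The Trial Design section states: "This is a randomized, prospective, multicenter, open-label, cross-over study". Under Randomization, allocation is by "blocked randomization" to PK measurements on "actual body weight followed by ideal body weight OR PK measurements based on ideal body weight followed by actual body weight". Block size and allocation ratio are not given.

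The Statistics section names the analysis of the first primary endpoint: "mean paired difference in recovery between the two methods (IBW vs. ABW dosing) by paired t-test", "or by Wilcoxon signed-rank test if recoveries are skewed". No period or sequence term appears there or in the power statement ("we estimate having 80% power"), which rests on 16 subjects, a mean reduction of 1 SD and an intra-class correlation of at least 0.2.

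Under Study design, the second dose follows the first by at least 48 hours for standard products, or "at least 72 hours for extended half-life products but no more than 60 days". The same 48- or 72-hour minimum applies before the first dose. The PK Protocol asks for the same laboratory for both doses, a baseline draw each time and, as far as possible, the same vial sizes and lots. Enrolment is up to 20 participants, with a minimum of 8.

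**The concern.** In a two-period cross-over, a shift between the first and second occasion enters the IBW–ABW difference with opposite signs in the two sequences. Balancing the order makes it possible to separate that shift from the dosing comparison, but a one-sample test on the differences does not use the order. The shift is counted as random error. If the completed sequences are unequal, part of it is also reported as an effect of the dosing strategy.

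This is not a detail left open for an analysis plan. The protocol names the test, and the named test has no period term. At stake are the width of the primary interval, its power and, with unequal sequences, its centre. With so few participants, one or two lost from one sequence are enough to unbalance the comparison.

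**Working it through.** **Inputs from the protocol.** N = 16, difference 1 SD of recovery, intra-class correlation 0.2, two sequences.

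**Assumptions.** Two-sided 5% level (the protocol states neither level nor sidedness), 1:1 allocation for the balanced case, and a period effect π (period 2 minus period 1) of 0 to 1 SD, because the documents give no value.

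**The stated power.** SD of the paired difference = √(2 × (1 − 0.2)) = 1.265. With N = 16 the standard error is 1.265/√16 = 0.316, the noncentrality is 1/0.316 = 3.16 on 15 df, and power is 84.0%. The smallest N reaching 80% is 15 (81.2%). The protocol's statement is therefore reproduced and slightly conservative.

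**How a period effect enters.** With true difference τ, the expected IBW−ABW difference is τ + π in the ABW-first sequence (n1 participants) and τ − π in the IBW-first sequence (n2). Hence:
- Mean of the plain differences = τ + π(n1 − n2)/n.
- Expected variance of the plain differences = 1.6 + 4·n1·n2·π²/(n(n − 1)).
- Adjusted estimate = half the difference between the two sequence means of the within-person period differences. It is unbiased for any π, with SE = (1.265/2)·√(1/n1 + 1/n2) on n − 2 df.

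Example at 8:8 with π = 0.5: variance = 1.6 + 4·8·8·0.25/(16·15) = 1.867, so the SD is 1.366 instead of 1.265.

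**Balanced sequences, 8:8.** The plain-test columns are from simulation with 100,000 runs per case.

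| Period effect (SD) | Plain: mean 95% half-width (SD) | Plain: type I error | Plain: power | Adjusted: power |
|---|---|---|---|---|
| 0 | 0.66 | 5% | 84% | 83.6% |
| 0.25 | 0.68 | 4.6% | 83% | 83.6% |
| 0.5 | 0.72 | 3.5% | 80% | 83.6% |
| 1 | 0.86 | 1.3% | 66% | 83.6% |

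The adjusted half-width is 0.67 SD and its type I error about 5% in every row. The plain estimate has no bias here.

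**Unequal sequences.** The bias of the plain estimate is π(n1 − n2)/n. At 10:6 this is π × 4/16, and at 5:3 it is π × 2/8, so a quarter of the period effect in both: 0.0625, 0.125 and 0.25 SD for π = 0.25, 0.5 and 1 SD. At 9:7 it is one eighth: 0.03, 0.06 and 0.125 SD. Its sign depends on the sign of π and on which sequence is larger.

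**Price of adjusting when π = 0.** Power falls from 84.0% to 83.6% at 8:8, from 84.0% to 81.2% at 10:6, and from 48.7% to 44.4% at 5:3.

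**The case against.** The strongest reply is that nothing in the documents shows a period effect. Each participant keeps the same product and laboratory, lots are matched where possible, and allocation is central and blocked. A post-recovery bleed or a missed recovery draw leads to a repeat within the two-month window. With balanced sequences the plain test is unbiased and conservative, so it creates no false claim. At 0.25 SD it loses about one point of power, and even at 0.5 SD it still has essentially the stated 80%.

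Adjustment is also not uniformly better. At 10:6 with a 0.25 SD effect, the plain interval is slightly narrower (0.68 against 0.69 SD) and the root-mean-square error slightly smaller (0.322 against 0.327). At 5:3 the two errors are about equal even at 0.5 SD (0.464 against 0.462).

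All of this stands and limits the size of the point. It does not remove it. The plain test relies on there being no period effect, an assumption the protocol never states. Failed repeats and drop-out can still leave unequal sequences.

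A reader might infer that the 48- or 72-hour gap proves a period effect, through factor left over from the first dose. The documents do not support that: the same minimum applies before the first dose, and a baseline is drawn each time. What is particular to the second period is carry-over that depends on which study dose came first, and a period term does not correct that. Imperfect vial or lot matching is no evidence either. Unless mismatches run in one direction by period, they are ordinary within-person error.

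**Conclusion.** The point holds as a conditional weakness in a fixed analysis choice, and the change is a cheap improvement. If there is no period effect, nothing is wrong with the planned test. If there is one, balanced sequences give an unbiased estimate with too wide an interval, and unequal sequences also bias the estimate by π(n1−n2)/n. The loss is small at 0.25 SD and substantial only towards 1 SD.

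A reader might conclude that the trial is underpowered or its primary result invalid. The documents support neither: the stated 80% is reproduced, and power drops clearly below it at 8:8 only for a period shift above about half an SD of recovery. The figures rest on the assumed two-sided 5% level, intra-class correlation 0.2, approximate normality and the assumed range of period effects.

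**What to change.** In the Statistics section, make the primary analysis the two-period cross-over comparison. Either compare within-person period differences between the two sequences, or fit a linear mixed model with fixed treatment and period and random participant. Report the IBW–ABW difference with its 95% confidence interval from that analysis. If recoveries are skewed, replace Wilcoxon signed-rank with a rank-sum test of the period differences between sequences; otherwise the same weakness returns through the fallback. State that the period term does not correct carry-over that depends on which dose came first.

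The cost is a sentence or two of text and one degree of freedom. No extra participants or data are needed. If there is no period effect, the price is about 0.4 points of power at 8:8 and about 3 to 4.5 points at 10:6 or 5:3. With 16 participants, power stays above the stated 80% at 8:8, 9:7 (83.1%) and 10:6 (81.2%).

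### The primary test switches to Wilcoxon on skewness of the recoveries, although both candidate tests use only the within-participant differences: a minor error in the stated rule

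*Protocol*

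**What the plan says.** The protocol's Statistics section assesses the first primary endpoint through "evaluation of the mean paired difference in recovery between the two methods (IBW vs. ABW dosing", and fixes the test as follows: "by paired t-test or by Wilcoxon signed-rank test if recoveries are skewed". The target is therefore a mean of within-participant differences, while the condition that selects the test is skewness of the recoveries themselves.

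The same section plans on 16 participants, with "80% power to detect a mean reduction of 1 standard deviation" at an intra-class correlation (ICC) of at least 0.2. Paired differences are mentioned again only as descriptive output should the study prove underpowered: "distributional summaries for each approach and for paired differences (including histograms". Nothing in the protocol ties the choice of test to the distribution of those differences.

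Enrolment may run from a minimum of 8 participants (Study design) to at most 20 (Recruitment).

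**The concern.** The paired t-test and the Wilcoxon signed-rank test both reduce each participant to one number, the difference between the two recoveries. The t-test needs those differences to be roughly normal and asks nothing of the recoveries' own distribution. A rule that looks at the recoveries can fail in two ways:

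- It can discard a t-test that was sound, because between-person skew common to both doses cancels on subtraction.
- It can keep the t-test when the differences are skewed but the recoveries do not look so.

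A second issue follows. The signed-rank test addresses the pseudo-median of the differences, which equals the mean only if the differences are symmetric. With asymmetric differences, the quantity behind the primary result depends on which branch is taken.

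At stake is whether the primary analysis answers the question the protocol sets, in a trial small enough that a skewness check is unreliable.

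**Working it through.** **1. The plan's own figure.** Inputs from Statistics: 16 pairs, a reduction of 1 SD of a single recovery, ICC 0.2. Alpha and sidedness are not stated; 0.05 two-sided is assumed.

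- SD of the difference = √(2 × (1 − 0.2)) = 1.265 SD
- Standardised paired effect = 1 / 1.265 = 0.791
- Noncentrality at n = 16: 0.791 × √16 = 3.16
- Power of the paired t-test (noncentral t, 15 df) = 84.0%; the smallest N reaching 80% is 15
- Power of the exact signed-rank test, by simulation = 80.9%

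The planned size therefore stands with either test.

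**2. How often the two triggers disagree.** Assumptions: log-normal recoveries, between-person CV 30%, within-person CV 15%, true ratio 0.85, n = 16. 'Skewed' means a D'Agostino skewness test at p < 0.05, and recoveries count as skewed if either dosing arm is flagged.

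- Recoveries flagged: 37% of trials (one arm alone: 23.6%)
- Differences flagged: 16%
- Triggers disagree: 35%

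Let R be trials flagged on recoveries only and D those flagged on differences only. Then R + D = 35% and R − D = 37% − 16% = 21%, so R = 28% and D = 7%. Most disagreement is an unneeded switch. The direction that keeps the t-test despite skewed differences occurs in about 7%.

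**3. What the rule does to the result in that setting.**

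- Power: 79.5% as written, 79.2% for the t-test alone, 80.1% with the trigger on differences
- Type I error: 4.9% as written against 5.3% with the trigger on differences (8,000 null trials); a separate run gave 5.1% as written
- The significance call differs from that of the t-test in about 2% of trials

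**4. Other distributions, n = 16** (40,000 trials per scenario; same flagging rule; power for a shift of 1; all entries %).

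| Scenario | Flagged on recoveries only | Flagged on differences only | Type I: as written / trigger on differences / t / Wilcoxon | Power: same order |
|---|---|---|---|---|
| Normal, ICC 0.2 | 9.1 | 4.3 | 5.1 / 5.3 / 5.1 / 4.6 | 83.7 / 84.1 / 84.0 / 80.9 |
| Log-normal, log SD 0.5, log-scale correlation 0.2 | 46.4 | 2.0 | 4.7 / 4.8 / 4.5 / 4.3 | 86.0 / 85.7 / 83.4 / 85.4 |
| Skewed participant effect, ICC 0.8 | 44.0 | 2.8 | 4.7 / 5.0 / 4.9 / 4.4 | all 100 |
| Skewed difference | 8.6 | 16.7 | 6.4 / 7.0 / 6.1 / 6.4 | 94.9 / 95.0 / 94.9 / 93.3 |

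At n = 16, moving the trigger to the differences changes type I error by at most 7.0 − 6.4 = 0.6 points and power by at most 84.1 − 83.7 = 0.4 points. Against the t-test alone, the largest power change is 86.0 − 83.4 = 2.6 points, in favour of the rule as written. At n = 8 the largest power gap between the two triggers is 60.5 − 58.2 = 2.3 points (skewed difference).

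**5. The estimand.** With log-normal data of this kind at n = 16, plus an assumed right-tailed BMI spread that scales the dose, the mean and pseudo-median differences were about 3–5% of the effect apart.

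**The case against.** The strongest reply is that the fault does almost no harm: the rule as written performs about as well as the t-test alone. That stands, and it sets the severity.

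It is also fair that the 37% against 16% contrast sets two looks at the recoveries (either arm) against one look at the differences. That is why the one-arm figure of 23.6% is given. Further, where the differences are symmetric, an unneeded switch leaves the target intact, because pseudo-median and mean then coincide. The estimand point is therefore confined to asymmetric differences.

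Three stronger readings are tempting and are not supported.

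- A reader might infer that the plan allows two primary p-values and a choice between them. It does not: it states in advance one test, and another on a condition. The missing cut-off for skewness may sit in a statistical analysis plan that is not shown.
- A reader might take "assuming approximate normality of recoveries" in the power paragraph as the same error repeated. It is not. That calculation is expressed in SDs of recovery and an ICC, for which normality of recoveries is the natural assumption; joint normality also makes the differences normal.
- A reader might quote a power loss from 84% to 81%. That compares the t-test with Wilcoxon in every trial. With normal data the rule switches in only about 10% of trials, and power falls from 84.0% to 83.7%.

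What does not stand is the defence that this is detail for an analysis plan. The protocol does not merely leave the condition open; it names the wrong quantity, and a plan that followed it would inherit the error.

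**Conclusion.** The point holds as a minor error in the stated rule. The protocol conditions the primary test on a quantity that neither test uses, and the Wilcoxon branch departs from the stated mean when the differences are asymmetric. In the log-normal setting at 16 participants the two triggers part in about 35% of trials, yet type I error and power move by about 1 point or less. The planned sample size is not in question.

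These sizes rest on assumed distributions and CVs, an assumed two-sided 5% level, and an assumed reading of 'skewed' as a 5% skewness test with either arm counting. The mismatch between condition and tests follows from the protocol text alone.

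**What to change.** In Statistics, delete the condition on skewed recoveries and name one primary method in advance. The closest to the present text is the paired t-test on the within-participant difference in recovery, with its mean and confidence interval, and the Wilcoxon signed-rank test as a sensitivity analysis only. If the sponsor prefers a ratio, the paired t-test on log recovery is an alternative. Its downside is that the estimand becomes a ratio instead of the mean difference now stated, and any gain in power depends on the data being close to log-normal.

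Moving the trigger to the differences is not enough. It would send skewed differences to the signed-rank test, which itself assumes symmetry, and in the skewed-difference scenario it gave 7.0% type I error against 6.1% for the t-test alone.

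The cost is protocol wording; the sample size need not change.
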